## 7.2. Exclusion criteria

Patients who meet any of the following criteria will be excluded from study entry:

1. Participants who have had chemotherapy, radiotherapy, or major surgery within 2 weeks (6 weeks for nitrosoureas or mitomycin C) prior to entering the study.
2. Patients that received during the metastatic disease setting any of the study drugs, palbociclib or binimatinib.
3. Participants receiving any other study agents concurrently with the study drugs. Zoledronic acid or denosumab for bone metastases, started at least 15 days prior to enrollment are allowed.
4. Participants with symptomatic brain metastases that require chronic steroids. Patients with a history of brain metastases are permitted to enroll as long as they have been treated, are off of steroids, and have been stable for a minimum of one month on imaging.
5. Irradiation of single lesions in the last 28 days prior to trial recruitment, if it is the only location of the disease and it has not progressed. Patients with radiated single lesions that has progressed are allowed.
6. Concurrent use of strong CYP3A4 inhibitors/inducers is prohibited due to drug-drug interactions with palbociclib. Moderate CYP3A4 inhibitors/inducers should be used with caution.
7. Uncontrolled intercurrent illness including, but not limited to:
  - a. ongoing or active infection requiring systemic treatment
  - b. symptomatic congestive heart failure
  - c. cardiac arrhythmia
  - d. psychiatric illness/social situations that would limit compliance with study requirements

- e. hypertension, defined as systolic blood pressure > 160 mmHg despite medical management
- f. myocardial infarction, unstable angina, coronary artery bypass grafting, coronary angioplasty, or stenting < 6 months prior to screening

8. History of QT syndrome, Brugada syndrome, known history of QTc prolongation, or Torsades de Pointes.

9. History of Gilbert's syndrome.

10. History of neuromuscular disorders that are associated with elevated CK (e.g. inflammatory myopathies, muscular dystrophy, amyotrophic lateral sclerosis, spinal muscular atrophy).

11. Previous or concurrent cancer except:

- a. cervical carcinoma in situ
- b. treated basal-cell carcinoma or squamous cell skin cancer
- c. any other cancer curatively treated > 3 years before the first study drug administration

12. Malabsorption syndrome or uncontrolled nausea, vomiting, or diarrhea that may interfere with the absorption of oral study medication in the opinion of the investigator.

13. Pregnant women or breast-feeding.

14. Known HIV-positive individuals on combination antiretroviral therapy.

15. Active hepatitis B virus (HBV; chronic or acute; defined as having a known positive hepatitis B surface antigen [HBsAg] test at the time of screening) or hepatitis C infection requiring treatment.

- a. Patients with past HBV infection or resolved HBV infection (defined as the presence of hepatitis B core antibody [HBcAb] and absence of HBsAg) are eligible if HBV DNA is negative.

- b. Patients positive for hepatitis C virus (HCV) antibody are eligible only if polymerase chain reaction is negative for HCV RNA.
- 16. Any condition that in the opinion of the investigator would interfere with evaluation of study treatment or interpretation of patient safety or study results, or inability to comply with the study and follow-up procedures.
- 17. Participation in another clinical study with investigational medicinal products within 4 weeks before the first study drug administration.
- 18. Clinically active infections within 2 weeks before the first study drug administration.
- 19. Treatment with therapeutic oral or i.v. antibiotics within 2 weeks before the first study drug administration. Patients receiving prophylactic antibiotics (e.g. for prevention of a urinary tract infection or to prevent chronic obstructive pulmonary disease exacerbation) are eligible.
- 20. Known hypersensitivity to any of the study drugs, study drug classes, or excipients in the formulation.
- 21. Current diagnosis of any retinal disorders including retinal detachment, retinal pigment epithelial detachment (RPED), serous retinopathy or retinal vein occlusion or risk factors for RVO (e.g., uncontrolled glaucoma or history of hyperviscosity or hypercoagulability syndrome).
- 22. Peripheral sensory neuropathy of CTCAE v.5.0 Grade 2 or higher
- 23. Major surgery, open biopsy or significant traumatic injury within 4 weeks before the first study drug administration (central line surgery is not considered major surgery).
- 24. Renal failure requiring peritoneal dialysis or hemodialysis.
- 25. Substance abuse, medical, psychological or social conditions that may interfere with the patient's participation in the study or evaluation of the study results.

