#### **5.1.3.6. Guidance for Investigators**

Binimatinib is an investigational drug for which limited safety data are available. It should be used with appropriate caution typical for an investigational drug.

Binimetinib has demonstrated an acceptable and manageable safety profile in nonclinical toxicology studies and clinical studies. As with any investigational drug, unexpected AEs may occur.

Available clinical data for binimetinib indicate a predictable safety profile consistent with those reported for other allosteric MEK1/2 inhibitors including the characteristic class effects of ocular toxicities, elevations of CK that are mostly asymptomatic, liver function test abnormalities (elevation of aspartate aminotransferase [AST], alanine aminotransferase [ALT] and total bilirubin), left ventricular dysfunction, skin toxicities including rash and acneiform dermatitis, hypertension, thromboembolic events, diarrhea, edema and hemorrhage. The majority of these toxicities are generally reversible and manageable by appropriate supportive medical care and/or dose modifications or discontinuation. Supportive therapy for the management of binimetinib-associated toxicities should be based on Investigator experience.

Binimetinib may cause fetal harm (teratogenicity) when administered to a pregnant woman. Binimetinib must not be used in pregnant women or nursing women, and the use of highly-effective contraception is recommended for male and female subjects participating in clinical studies. Additionally, women of childbearing potential must be advised to use highly effective contraception.

Ocular toxicities can occur with binimetinib administration. Patients should be assessed for symptoms of new or worsening visual impairment. Patients with a history or current evidence of retinal vein occlusion (RVO) or risk factors for RVO (e.g., uncontrolled glaucoma or history of hyperviscosity or hypercoagulability syndrome) should be excluded from studies with binimetinib.

New onset hypertension, or worsening of pre-existing hypertension, can occur with the use of binimetinib. Patients should be monitored for hypertension and treated as needed with standard anti-hypertensive therapy.

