### Recommended dose modifications for binimetinib for selected adverse reaction.

Severity of adverse reaction a	Binimetinib
Cutaneous reactions	
• Grade 2	Binimetinib should be maintained. If rash worsens or does not improve within 2 weeks with treatment, binimetinib should be withheld until improved to Grade 0 or 1 and then resumed at the same dose if first occurrence or resumed at a reduced dose if recurrent Grade 2.
• Grade 3	Binimetinib should be withheld until improved to Grade 0 or 1 and resumed at the same dose if first occurrence or resumed at a reduced dose if recurrent Grade 3.
• Grade 4	Binimetinib should be permanently discontinued.
Ocular events	
• Symptomatic retinal pigment epithelial detachments (RPED) (Grade 2 or 3)	Binimetinib should be withheld for up to 2 weeks and ophthalmic monitoring should be repeated including visual acuity assessment. 

• If improved to Grade 0 or 1, binimetinib should be resumed at same dose.

• If improved to Grade 2, binimetinib should be resumed at a lower dose.

• If not improved to Grade 2, binimetinib should be permanently discontinued.

• Symptomatic RPED (Grade 4) associated with reduced visual acuity (Grade 4)	Binimetinib should be permanently discontinued.
• Retinal vein occlusion (RVO)	Binimetinib should be permanently discontinued.

Severity of adverse reaction a	Binimetinib
Cardiac events	

 
Grade 2 Left ventricular ejection fraction (LVEF) decrease or asymptomatic, absolute decrease in LVEF of greater than 10 % from baseline that is below lower limit of normal (LLN)
 
	
LVEF should be evaluated every 2 weeks.
 
 
If asymptomatic: Binimetinib should be withheld for up to 4 weeks. Binimetinib should be resumed at a reduced dose if all of the following are present within 4 weeks: 
 
LVEF is at or above the LLN
 
Absolute decrease from baseline is 10 % or less.
 
 
 
If the LVEF does not recover within 4 weeks, binimetinib should be permanently discontinued.
 

 
Grade 3 or 4 LVEF decrease or symptomatic left ventricular dysfunction (LVD)
 
	
Binimetinib should be permanently discontinued. LVEF should be evaluated every 2 weeks until recovery.

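### Exclusion criterion 21 leaves out a history of retinal vein occlusion (RVO), although the protocol's own guidance in 5.1.3.6 directs that such patients be kept out of binimetinib studies

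*Protocol*

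**What the plan says.** Protocol 5.1.3.6, Guidance for Investigators, describes the ocular risk of binimetinib. It says that "Patients with a history or current evidence of retinal vein occlusion (RVO) or risk factors for RVO" (with examples in brackets) "should be excluded from studies with binimetinib".

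The entry rule is exclusion criterion 21 in Protocol 7.2. It excludes "Current diagnosis of any retinal disorders including retinal detachment, retinal pigment epithelial detachment (RPED), serous retinopathy or retinal vein occlusion or risk factors for RVO", with the same bracketed examples. The synopsis (Protocol 1.13.2) and SAP 3.9 carry the same wording.

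Two general criteria in the same list could also apply. Criterion 16 covers "Any condition that in the opinion of the investigator would interfere with evaluation of study treatment or interpretation of patient safety or study results". Criterion 25 begins "Substance abuse, medical, psychological or social conditions that may interfere with" and goes on to participation in the study or evaluation of its results.

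**The concern.** The guidance excludes on past or present RVO, whereas the criterion excludes on present RVO only. Sites screen against the numbered list, which Protocol 7.2 presents as the conditions that exclude a patient from entry. Section 5.1.3.6 is background text and is not part of that list. A patient whom the protocol's safety guidance says should not receive binimetinib could therefore pass every explicit entry criterion, and the 8 sites could decide the same case differently.

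What is at stake is the safety of an individual patient and consistent eligibility decisions. No estimate or test in the trial depends on this point.

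**Working it through.** No arithmetic applies, so the check is a comparison of texts.

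**Step 1. Set the guidance beside the criterion.**

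| Group to exclude | Protocol 5.1.3.6 | Criterion 21 (7.2, 1.13.2, SAP 3.9) |
|---|---|---|
| History of RVO | Named | Not named |
| Current RVO | Named | Named, as a current diagnosis |
| Risk factors for RVO | Named, with examples | Named, with the same examples |

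One of the three groups is missing. The three copies share one wording, so this is one omission and not three.

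**Step 2. Does the risk-factor clause cover past RVO?** The clause reads "risk factors for RVO (e.g., uncontrolled glaucoma or history of hyperviscosity or hypercoagulability syndrome" and is open-ended, so an investigator may read a previous RVO into it. But past RVO is not among the examples, and 5.1.3.6 lists history of RVO separately from risk factors. The protocol itself therefore does not treat the second as including the first. Within the clause, the word *history* is attached only to hyperviscosity and hypercoagulability syndromes.

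**Step 3. Does another criterion cover it?** None of the other inclusion or exclusion criteria names past RVO. Criteria 16 and 25 allow exclusion on a judgement that the condition would or may interfere. Neither makes past RVO an exclusion in itself.

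**Step 4. Could the current-only wording be deliberate?** The documents give no reason for narrowing the exclusion. Criteria 8, 9 and 10 of the same list are worded as history criteria, so a site will naturally read criterion 21 as current only. For a history of venous thromboembolism, 5.1.3.6 asks only for caution, whereas for a history of RVO it asks for exclusion. The guidance therefore draws that distinction on purpose, and the entry list does not carry it through.

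**Step 5. Who falls through?** A patient with past RVO that has resolved, no retinal disorder at the screening eye examination (Protocol 10.1), and no recognised risk factor. Residual retinal disease found at screening is already excluded by criterion 21.

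**The case against.** The strongest reply is that investigators are not left without direction. Section 5.1.3.6 belongs to the same approved protocol, is addressed to investigators and covers this exact case. Read together with the open risk-factor list and criteria 16 and 25, it gives a site both the instruction and the means to exclude. This largely stands. A reader might infer that past RVO is left to unguided judgement, and that would be wrong. What remains is that the instruction sits outside the list against which eligibility is checked, and applying it takes an inference that a single phrase would remove.

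A second reply is that eye monitoring is close. Under Protocol 10.2, patients are asked about vision at every visit. Examinations are weekly in cycle 1, every two weeks in cycle 2 and every 4 weeks after that. This is true, and it limits harm after exposure. It does not do what 5.1.3.6 asks, which is to prevent the exposure.

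A reader might also want to argue that the protocol treats RVO with special strictness once it occurs, because the dose-modification table in 9.3.2 has an RVO row with no grade threshold and the action "Binimetinib should be permanently discontinued". The documents do not support that argument, because they are mixed. Protocol 8.1 names RVO among the retinal events of Grade 2 or higher after which treatment may resume one dose level lower, following recovery and discussion with the sponsor. Protocol 10.2 lists it among Grade 1 events followed by eye examinations on day 1 of every cycle, which implies continued treatment. The case for the change rests on the entry guidance alone.

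**Conclusion.** The mismatch is real and is wrong as written: criterion 21 omits one of the three groups that the protocol's guidance says to exclude. It is a narrow safety and eligibility inconsistency, worth correcting but low in priority.

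The documents give no frequency of past RVO in this population. A reader might want an expected count or a probability that at least one patient is affected, but any such figure would reflect only the frequency assumed. That few or none of the 25 patients would be affected is a judgement. It rests on how many conditions must coincide: past RVO, full resolution, no recognised risk factor, and an investigator who does not act on 5.1.3.6. The 3-month PFS endpoint, the sample size and the planned analysis are unaffected.

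**What to change.** Reword criterion 21 in Protocol 7.2 and 1.13.2, and carry the change to SAP 3.9, so that it has three limbs:

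- history or current evidence of RVO;
- current diagnosis of any other retinal disorder, with retinal detachment, RPED and serous retinopathy kept as the named examples;
- risk factors for RVO, with the present examples unchanged.

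This keeps every existing exclusion and adds the missing one. The mismatch should not be settled the other way, by deleting the reference to history from 5.1.3.6.

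No new procedure is needed, because a complete medical history and an eye examination are already part of screening (Protocol 10.1). Under Protocol 14.3 a change to the approved protocol needs an amendment with a favourable ethics opinion and health-authority authorisation, so it is best bundled with the next one. It helps only while patients are still being enrolled. The study calendar planned last inclusion for the fourth quarter of 2021, and the documents do not show whether enrolment was still open after that.

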### **7.3. Randomization procedures**

Not applicable. Single arm, open-label study.

### **7.4. Blinding procedures**

Not applicable. Open-label study.

## **8. WITHDRAWAL CRITERIA**

### **8.1. Reasons for Withdrawal**

Patients have the right to voluntarily withdraw from the study at any time for any reason. In addition, the investigator has the right to withdraw a patient from the study at any time.

Every effort should be made to obtain information on patients who withdraw from the study. The primary reason for withdrawal from the study should be documented on the appropriate eCRF.

Reasons for withdrawal from the study may include but are not limited to the following:

- Unacceptable toxicity.
- If, in the investigator's opinion, continuation of study would be harmful to the patient's well-being.
- Any toxicity requiring dose reduction below 30 mg/BID of binimetinib or 75 mg daily of palbociclib.
- Any toxicity requiring dose interruption longer than 28 days to resolve to Grade 1 or better.
- Any other potential adverse reaction deemed sufficiently serious to warrant discontinuation of treatment by the investigator or his designated associate(s).
- Any decrease in visual acuity, or symptomatic or asymptomatic retinal disorders including retinal detachment / retinal pigment epithelial detachment / serous retinopathy / **retinal vein occlusion** classified analog to CTCAE v.5 as Grade 2 or higher. Based on the individual benefit risk assessment and after discussion with the sponsor, patient may interrupt treatment until recovery to at least Grade 1 and then treatment may be resumed at one dose level below.
- Grade 4 non-hematological toxicity (laboratory abnormalities of any grade will not be considered toxicity unless deemed clinically significant by the investigator).
- Any AE that meets criteria for discontinuation.

- Subject noncompliance that warrants withdrawal in the opinion of the investigator or sponsor.
- Initiation of alternative anticancer therapy including another investigational agent.
- Confirmation of PD and investigator determination that the subject is no longer benefiting from treatment with study treatment.

If the administration of any of the study drugs has to be stopped, the site principal investigator will consult with the sponsor to withdraw the patient from the study (depending on the duration of treatment, if she has benefit, if the benefit is attributed to the suspended drug, etc.).

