## 6. STUDY DESIGN

## 6.1. Overall design

This is an interventional, prospective, multicentric, single-arm, open label, phase IB clinical trial.

The following scheme depicts the basic trial design.

Patients diagnosed of metastatic or locally advanced non-curable TNBC that have received at least one treatment regimen for advanced disease will be candidates for the trial. A fresh tumor sample will be obtained in order to determine the phosphoproteomic profile of the tumor preferably obtained after last treatment or the most recent sample as possible (from metastatic site or first diagnosis according to sample availability) prior to study inclusion. If the patient has not a tumor sample available prior to study inclusion, the patient will not be allowed to participate in the study. Activation of the two kinases of interest will be determined centrally at CNIO. Only patients with scores above the upper quartile of at least one of them will be candidates (according to our series, approximately 40% of the patients are positive for CDK4/6 and/or ERK).

Patients will then start treatment with continuous oral binimetinib 45 mg/BID and palbociclib 100 mg daily, 21 days on / 7days off, until disease progression. Tumor evaluation will be performed every 8 weeks. Study treatment will continue until disease progression, unacceptable toxicity, intercurrent serious disease, consent withdrawal or investigator's decision.

If treatment tolerance is good (no side effects or at most tolerable grade 1 side effects) after a full cycle (28 days) patients will be allowed to escalate palbociclib to 125, according to the study investigators' decision. Alternatively, patients with non- tolerable grade 2 events will resume at 30 mg/BID of binimetinib upon recovery, maintaining palbociclib at 100 mg 21-on/7-off. Depending on the side-effects, in case of clear relationship with palbociclib is established, palbociclib -instead of binimetinib – will be reduced to 75 mg daily.

The study will be conducted at 8 Spanish sites and will enroll 25 patients.

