## **10.2. Study treatment visits**

Study patients will be evaluated weekly during the first 2 months and every 2 weeks thereafter.

The following procedures will be performed during study treatment:

- Tumor evaluation: PET-CT, CT and/or MRI (every 8 weeks)
- Physical examination: will be performed at screening and thereafter targeting symptoms in subsequent study visits
- Ophthalmological examination: Ask patient for changes in vision at every visit. If change in vision is reported, an ophthalmological examination must be performed preferably within 3 days. Ophthalmologic examination will be performed weekly during first cycle, biweekly during second cycle and every 4 weeks thereafter. Particularly for patients who experience any decrease in visual acuity, or symptomatic or asymptomatic retinal disorders including retinal detachment / RPED / serous retinopathy / retinal vein occlusion (Grade 1 analog to CTCAE v.5) have to undergo ophthalmologic examinations on day 1 of every cycle.
- Weight: in all study visits

- Vital Signs: pulse, blood pressure and temperature; every week during first two cycles, and days 1 and 15 of each cycle thereafter
- ECOG performance status (day 1 of every cycle)
- 12-lead ECG: if clinically indicated
- ECHO/MUGA: before start binimetinib treatment, 4 weeks after the start of treatment and every 12 weeks thereafter.
- Hematology: every week during first two cycles, and days 1 and 15 of each cycle thereafter
- Biochemistry: every week during first two cycles, and days 1 and 15 of each cycle thereafter. Safety laboratory tests can be collected up to 2 days prior to drug administration.
- TSH, fT3 y fT4: day 1 of every cycle. Free T3 and free T4 will only be measured if TSH is abnormal.
- Coagulation: day 1 of every cycle
- Urinalysis: day 1 of every cycle
- Serologies: if clinically indicated
- Pregnancy Testing: every 4 weeks (day 1 of each cycle). Pre-menopausal women of childbearing potential only
- Adverse events: in all study visits
- Concomitant medications: in all study visits
- Blood sample: two CPT tubes of 7 ml will be obtained before treatment administration at D1C1 and D1C2.

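### Section 8.1 lets treatment restart after retinal vein occlusion without excluding binimetinib, which 9.3.2 stops for good; the two sections also differ on restarting after symptomatic RPED

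*Protocol*

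**What the plan says.** Protocol 8.1 lists reasons for withdrawal. One bullet covers loss of visual acuity and retinal disorders of Grade 2 or higher, and names retinal detachment, RPED, serous retinopathy and RVO together. The same bullet attaches an exception to the whole list. "Based on the individual benefit risk assessment and after discussion with the sponsor", it says, the "patient may interrupt treatment until recovery to at least Grade 1 and then treatment may be resumed at one dose level below". The word used is treatment; neither drug is named or left out. A later bullet in the list reads "Any AE that meets criteria for discontinuation", with no pointer to another section.

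Protocol 9.3.2 has a binimetinib dose-modification table with its own ocular rows. For RVO, with no grade given, the action is "Binimetinib should be permanently discontinued", and there is no route back. For symptomatic RPED of Grade 2 or 3, binimetinib is held for up to two weeks and the next step depends on recovery. "If improved to Grade 0 or 1, binimetinib should be resumed at same dose"; if the event has improved only to Grade 2, binimetinib restarts at a lower dose; if it has not improved even that far, it is stopped.

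Protocol 9.2 and the last paragraph of 8.1 allow a patient who stops one drug to continue on the other by arrangement with the sponsor.

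**The concern.** RVO is named in both places, so this is not simply a general rule giving way to a specific one. A site that turns to 8.1 finds a written route back to treatment after RVO; a site that turns to 9.3.2 finds a permanent stop for one of the two drugs. If the 8.1 route were used for binimetinib, a patient could be re-exposed to it after an event for which the protocol's own table forbids this. The protocol also treats RVO as a reason to keep patients off the drug: 5.1.3.6 advises excluding anyone with past or current RVO from binimetinib studies, and exclusion criterion 21 bars current RVO and its risk factors.

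For symptomatic RPED the stake is smaller but more direct. The two sections give different instructions for the same patient on the same day, both on whether to restart and on the dose.

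**Working it through.** The plan gives no figure to reproduce here. The check sets the two sections side by side, with one line of dose arithmetic.

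| Event and status | 8.1 eye bullet | 9.3.2 table | Can both be followed? |
|---|---|---|---|
| RVO of Grade 2 or higher, recovered to Grade 1 or better | Treatment may restart one dose level lower, after sponsor discussion; no drug excluded | Binimetinib stopped permanently | Only if the restart is limited to palbociclib |
| Symptomatic RPED, Grade 2 or 3, recovered to Grade 0 or 1 | Restart one dose level lower | Restart binimetinib at the same dose | No, if the 8.1 reduction applies to binimetinib |
| Symptomatic RPED, Grade 2 or 3, improved only to Grade 2 | No restart until Grade 1 or better | Restart binimetinib at a lower dose | No |

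**Does treatment in 8.1 include binimetinib?** Three pieces of text bear on this.

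1. Section 5.1.3.6 presents eye toxicity as an effect of binimetinib: "Ocular toxicities can occur with binimetinib administration".
2. Section 6.1 makes binimetinib the drug reduced by default. After a Grade 2 event that is not tolerated, patients "will resume at 30 mg/BID of binimetinib upon recovery, maintaining palbociclib at 100 mg 21-on/7-off". Palbociclib is reduced instead only when the event is clearly related to it. This rule is not specific to the eye.
3. The 8.1 exception is one sentence covering the whole list. For RPED, 9.3.2 plainly expects binimetinib to restart, so the sentence has to be able to cover binimetinib there. It cannot cover binimetinib for RPED and exclude it for RVO without saying so.

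**Which section prevails?** Neither refers to the other on this point. The discontinuation bullet in 8.1 may be meant to bring in the table, but it does not say so and does not switch off the RVO wording in the same list.

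**Dose difference at an RPED restart.** Inputs: starting dose 45 mg twice daily and reduced dose 30 mg twice daily (9.1.1.4 and 9.3.2).

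- Same dose: 2 × 45 = 90 mg/day.
- One level below: 2 × 30 = 60 mg/day.
- Relative difference: (90 − 60) / 90 = 33.3%.

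This is the difference on the day of restart for a patient who was on the starting dose.

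**The case against.** The best case for the plan is that the RVO texts can be reconciled. RVO stands in 8.1 first as a reason to withdraw; the exception is permissive and requires sponsor discussion; and 9.2 provides for continuing on one drug. On that reading binimetinib stops, and palbociclib may continue at a reduced dose (100 to 75 mg). A site that follows 9.3.2 breaks nothing in 8.1. Harm would require both investigator and sponsor to overlook an explicit RVO row. Exclusion 21, questions about vision at every visit and prompt examination of any reported change lower the risk further. The table is also headed as recommended, and under 8.1 one sponsor would see every restart.

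Much of this stands. It confines the RVO conflict to the case where the exception is used for binimetinib. It does not remove it, because the palbociclib-only reading is nowhere written and does not fit the same sentence's use for RPED. Sponsor discussion is a safeguard, but the sponsor has no settled rule to apply, and the table's RPED row does not mention that discussion. The recommended heading softens the table without reconciling it with 8.1.

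A reader might infer more than the documents support:

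- **That 10.2 expects patients to stay on binimetinib after Grade 1 RVO**, because it sets eye examinations on day 1 of every cycle for them. The study schedule already gives all patients an examination on day 1 of each cycle. The sentence adds nothing about restarting either drug.
- **That the RPED dose gap lasts at least 28 days**, from the re-escalation condition in 9.1.1.4. That section does not say when its 28 days begin, and 9.3.2 lets re-escalation be considered once the reaction is effectively managed, with no minimum time. No cumulative dose difference can be derived.
- **That the different CTCAE versions** (5 in 8.1, 4.03 under the table) make the conflict worse. The documents show no difference in the relevant grade definitions.

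**Conclusion.** The point holds in a limited form. For RVO there is one conflict, which arises only if the permissive 8.1 exception is applied to binimetinib. Section 11.3.6 calls RVO uncommon, so the case may not occur among 25 patients, but the text as written permits a restart that the table rules out. For symptomatic Grade 2 or 3 RPED there are two conflicts: the dose after recovery to Grade 0 or 1 (90 against 60 mg/day at restart from the starting dose) and whether restart at Grade 2 is allowed. The dose comparison assumes that the one-level reduction in 8.1 falls on binimetinib, which 5.1.3.6 and 6.1 support but 8.1 does not state.

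This is a patient-safety and dosing-consistency issue. It would be wrong to infer that the protocol directs sites to restart binimetinib after RVO: it only fails to exclude it. Nor do the documents give a rate of symptomatic Grade 2 or 3 RPED, or any basis for claiming an effect on PFS.

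**What to change.** 1. In the 8.1 eye bullet, take RVO out of the restart exception and add: *Retinal vein occlusion of any grade: permanently discontinue binimetinib (see 9.3.2); continuation on palbociclib alone to be agreed with the sponsor under 9.2.*

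2. State one restart rule for symptomatic Grade 2 or 3 RPED and use it in both 8.1 and the 9.3.2 table. It should name the drug that is lowered, the dose after recovery to Grade 0 or 1, and whether restart at Grade 2 is allowed. The safer default is the 8.1 rule, namely recovery to Grade 1 or better and then binimetinib 30 mg twice daily, unless the clinical team documents a reason for preferring the table's rule.

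Keep the cross-reference to these two events. A general statement that 9.3.2 prevails could weaken the separate 8.1 rule on withdrawal for Grade 4 non-haematological toxicity.

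The cost is a protocol wording amendment and a letter to sites. The sponsor gives up the option of resuming binimetinib after RVO. Sample size and analysis are unchanged.
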